## 7.7 Statistical Analyses Methodology

Statistical analyses will be performed using SAS software Version 9.2 or later. Continuous variables will be summarized using descriptive statistics, including but not limited to the mean, the standard deviation, median, minimum value, and maximum value. Categorical variables will be summarized using frequency counts and percentages. All data collected across the 4 treatment groups throughout the study will be listed in data listings.

All statistical tests will be 2-sided and performed using a 5% significance level, leading to 95% (2-sided) CIs. As the primary efficacy endpoint is analyzed at the interim analysis and at the end of the study, multiplicity will be addressed by using a combination test to combine the results (see Section 7.7.1). A hierarchical method will be employed to address any multiplicity arising from the analysis of the key secondary endpoint. In other words, the formal analysis of this endpoint will be performed only if a statistically significant result is obtained from the combination test analysis of the primary endpoint. All analyses performed on the other secondary endpoints are for exploratory purposes only; therefore, no further multiplicity adjustment is required.

The combined analysis of patients from Parts 1 and 2 rests on the assumption that patients recruited in each part of the study will belong to the same overall patient population. To check this assumption, data related to the baseline characteristics (for all 4 treatment groups) will be repeated for Part 1 and Part 2. If any notable differences are observed, then the combined analysis of Parts 1 and 2 will need to be interpreted with caution and further exploratory analysis will need to be conducted to investigate the possible causes.

The assumption of a consistent treatment effect across Parts 1 and 2 will be investigated by repeating the primary and key secondary efficacy analyses (for the optimal recAP dose and placebo treatment groups) for Part 1 and Part 2. Again, any notable differences will lead to the combined analysis of Parts 1 and 2 being interpreted with caution and further exploratory analyses conducted to investigate the possible causes.

Further details of the statistical analyses, methods, and data conventions will be described in the SAP.

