Please note that any patients who do not receive any dose of study drug will be excluded from the safety and PP analyses, and therefore do not need to be considered in the [Table 4-1](#). Dose windows were constructed in line with the weight ranges and corresponding pre-calculating volumes displayed in [Table 15-3](#). See [Section 15.3](#) for full justification of these windows.

Statistical Analysis

All statistical tests will be two-sided and performed using a 5% significance level, displaying 95% two-sided confidence intervals (CIs), unless specifically stated otherwise. As the primary efficacy endpoint is analyzed at the interim analysis and at the end of the study, multiplicity will be addressed by using a combination test to combine the results (see [Section 8.1.1](#)). A hierarchical method will be employed to address any multiplicity arising from the analysis of the key secondary endpoint. In other words, the formal analysis of this endpoint will be performed only if a statistically significant result is obtained from the combination test analysis of the primary endpoint. All analyses performed on the other secondary endpoints are for exploratory purposes only; therefore, no further multiplicity adjustment is required.

All analyses will be undertaken using SAS[®] Version 9.2 (SAS Institute, Inc, Cary, North Carolina) or later.

Weight

Body weight (in kg or lb) will be measured or estimated at screening. Weight will be displayed in kg and derived from lb as:

$$Weight[kg] = \frac{Weight[lb]}{2.2046}$$

Temperature

Temperature (in °C or °F) will be measured from Day 1 – Day 28. Temperature will be displayed in °C and derived from °F as:

$$Temperature[°C] = \frac{Temperature[°F] - 32}{1.8}$$

Laboratory Data

For laboratory data that are recorded as values of '<x' and '>x' where x is any numeric value, the numeric part after the '>' and '<' (i.e. x) will be used for summarizing and in graphical presentations. In addition the numeric part will be used in the derivation of the quartile-based subgroup definitions.

In the tables where serum creatinine or CRP data are presented, if a subject has missing baseline central laboratory measured serum creatinine or CRP values, but has available baseline local laboratory measured values then the local laboratory values will be used to

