4.1. Sample Size

A sample size of $n_1 = 30$ patients per treatment group in Part 1 with an additional $n_2 = 85$ patients recruited to each of the optimal recAP dose and placebo treatment groups in Part 2 (for a total sample size of $n = 290$ patients) is planned. Recruitment will continue during the interim analysis, so the total number of patients will exceed 290. Custom programmed simulations were performed using SAS[®] Version 9.2 (SAS Institute, Inc, Cary, North Carolina) to determine power and type I error rate of the chosen sample size and design under a number of different dose response scenarios. Each scenario assumed a standard deviation of 49 mL/min for the primary endpoint (area under the time-corrected endogenous creatinine clearance curve from Day 1 to Day 7 [AUC₁₋₇]) with an assumed response of 60 mL/min for the placebo group, and between 60 mL/min (no treatment effect) and 79 mL/min (strong treatment effect) for the recAP dose groups.

Fifty-thousand simulations were performed to show that the 1-sided type I error rate is 2.4% (and hence is well controlled at the 1-sided 2.5% significance level). The power was defined as the probability of rejecting the null hypothesis (of no difference between treatment groups) when 1 or more recAP dose groups have an effective treatment effect, defined as a response of 69.5 mL/min. This was investigated across 7 scenarios with 10 000 simulations performed for each. In the most realistic scenarios (with strong treatment effects, i.e., responses of 79 mL/min for the medium and high recAP dose groups and a varying response of between 60 mL/min and 79 mL/min for the low-dose group) the chosen design achieved power of between 79% and 86%. This dropped to 66% to 67% for other scenarios where only the high recAP dose group had a strong treatment effect.

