8.1.1. Primary Analysis

The primary efficacy analysis will be an analysis of variance (ANOVA) of the area under the time-corrected endogenous creatinine clearance curve from Day 1 to Day 7 with treatment and site as explanatory variables.

For all patients recruited up to the interim analysis, the primary efficacy analysis will be conducted for the ITT Combined Set at the interim analysis (which is identical to the ITT Part 1 Interim set at the time of the interim analysis) where AUC_{1-7} will be compared between the 3 active treatment groups and placebo. This analysis will be considered in conjunction with the safety data to determine the optimal recAP dose for use in Part 2.

The primary efficacy analysis will be conducted for the ITT Part 2 Set, PP Day 1 – 7 Part 1 and PP Day 1 – 7 Part 2 Set where AUC_{1-7} will be compared between the optimal recAP dose and placebo (for the PP Day 1 -7 Combined Set, each dose of recAP will be compared to Placebo). Also, all doses combined will be compared to Placebo.

Confirmatory testing of the single hypothesis comparing optimal dose with placebo will be based on a closed-testing procedure. This hypothesis will be rejected at the 5% significant level if it and all intersection hypotheses involving it are all rejected at the 5% significance level. The testing strategy used to combine results from Parts 1 and 2 will be a combination test based on the inverse normal method, with the test statistic of the combination test calculated as ([Bauer and Köhne 1994](#)):

$$\sqrt{\frac{n_1}{n}} \Phi^{-1}(1 - p_1) + \sqrt{\frac{n_2}{n}} \Phi^{-1}(1 - p_2)$$

where n_1 and n_2 are the sample sizes per group in interim analysis at Part 1 and in Part 2, respectively, $n = n_1 + n_2$, Φ refers to the standard normal distribution, and p_1 and p_2 are the one-sided p-values from interim analysis at Part 1 and from Part 2, respectively. For the intersection hypotheses, p_1 is the Dunnett adjusted one-sided p-value in Part 1 (for the optimal dose selected), and p_2 is the one-sided unadjusted p-value to compare optimal dose with placebo in Part 2 for all hypotheses.

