Results from the primary analysis for interim analysis at Part 1 and for Part 2 will include least square means for each treatment and the difference in least squares means between the treatment groups will also be presented along with the associated 95% CI. P-values will be presented for least square mean treatment differences. The one-sided p-value for the combined analysis will be presented with the sample sizes and one-sided p-values from the interim analysis at Part 1 and at Part 2.

Descriptive statistics for the primary endpoint and mean standardized endogenous creatinine clearance at Day 1 to Day 7 will also be presented in a summary table by

treatment. This will be presented for all four treatment groups for the ITT Combined, ITT part 1 Interim, PP Day 1-7 Part 1, and also for the optimal recAP dose and placebo treatment groups for the ITT Part 2 and PP Day 1-7 Part 2 Sets. Analysis on the PP Set will be used as a supplement to the ITT analysis. The ITT Part 1 Interim Set (for all four treatment groups) will also be produced to help check the assumption of the combined analysis that patients recruited in each part of the study belong to the same overall patient population.

The primary endpoint, AUC_{1-7} , and standardized endogenous creatinine clearance at Day 1 to Day 7 will be listed.

A time-course plot of standardized endogenous creatinine clearance with associated error bars on each day will be presented for the optimal recAP dose and placebo groups. This plot will be repeated three times using different selection criteria for the data based on data imputation and adjudication of creatinine clearance data:

- 1) Including only calculated values (i.e. no imputed values)
- 2) Including all (non-adjudicated) calculated and imputed values
- 3) Including only adjudicated calculated and imputed values

The combined ITT analysis primary endpoint summary and analysis will be repeated as a supportive sensitivity analysis, excluding patients who died before day 8, with SAS[®] output from Part 1 and Part 2 models included on the primary combined analysis output. Additionally, descriptive statistics for the primary endpoint and mean time-corrected endogenous creatinine clearance at Day 1 to Day 7 will be presented in a summary table for the ITT Combined Set by treatment group and subgroup category, defined in [Section 8.1.5](#).

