8.2. Secondary Efficacy Endpoint

8.2.1. Key Secondary Efficacy Endpoint

The key secondary endpoint is RRT incidence during the period Day 1 (after first treatment) to Day 28, inclusive. Should a patient die or withdraw from the study during this period without recording RRT incidence, he or she will be counted as having not required RRT.

Analysis of this key secondary endpoint will be performed for the ITT Combined Set and PP Day 1– 7 Combined Set.

The optimal recAP dose will be formally compared with placebo using a logistic regression model with treatment group and site as explanatory variables, if a statistically significant result is obtained from the combination test analysis of the primary endpoint. Otherwise the results will be reported as exploratory analyses only. In the event that there are issues with the model (e.g. quasi-complete separation of data points) the reason will be investigated and if needed, site will be removed from the model. In this case, it will be documented as a deviation from the protocol in order to avoid a questionable validity of the model fit.

This endpoint will additionally be summarized for all four treatment groups using counts and percentages. The odds ratio and associated 95% confidence interval from the comparisons of the optimal recAP dose versus Placebo will also be presented. The counts and percentages will also be presented for ITT Part 1 Interim Set and ITT Part 2 Set separately.

The analysis of this key secondary endpoint will be repeated excluding patients who died or withdrew from the study prior to completion of this 28 Day period. If a statistically significant result is obtained from the combination test analysis of the primary endpoint and the key secondary endpoint, the optimal recAP dose will be formally compared with placebo using a logistic regression model with treatment group and site as explanatory variables.

The analysis of RRT incidence for the ITT Combined Set will also be presented for the supportive factor analysis as described in section 8.1.5 for the primary endpoint.

RRT data will be presented in a listing.

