3.0 (25SEP2017)	2.3 8.1.5	Added ≥ 24 hour category for Time from first diagnosis of SA-AKI to start of treatment
3.0 (25SEP2017)	3.2.4	Kaplan-Meier will be done once for time to discharge from ICU and time to discharge from Hospital (removed separate analyses for Days 1-28 and Days 1-90)
3.0 (25SEP2017)	4	Definition of baseline updated for subjects who were randomized but not treated
3.0 (25SEP2017)	4	Added text on handling of < or > for laboratory values and added Table 4-2 Serum Creatinine and CRP laboratory conversions
3.0 (25SEP2017)	4.3.3.4 5.1 8.2.1	Removed PP Day 1-28 Set and replaced with PP Day 1-7 Combined Set where appropriate
3.0 (25SEP2017)	6.1	Race category updated from ‘Not Applicable’ to ‘Not Collectable’.
3.0 (25SEP2017)	6.2	Local lab values for serum creatinine will be used if central lab values are not available.
3.0 (25SEP2017)	6.2	CKD-EPI formula will no longer be used if creatinine clearance values are not available.
3.0 (25SEP2017)	8.1	Added rule for standardized creatinine clearance calculation that when urine volume is <30ml/24 hour then standardized creatinine clearance will be set to 1ml/min.
3.0 (25SEP2017)	8.1.1	Clarification added that the p-values used in the equation for the combination test are 1-sided p-values.
3.0 (25SEP2017)	8.1.1	Time course plot for creatinine clearance will be repeated three times based on different selection based on imputation and adjudication of creatinine clearance data.
3.0 (25SEP2017)	8.1.2	Removed AUC from list of data reviewed by adjudication committee.
3.0 (25SEP2017)	8.1.5	All baseline variables of interest /subgroups will be used as additional covariates in the statistical models (not as by-groups). In addition, as a result, Baseline AKIN stages 2 and 3 will not be combined into an additional group.
3.0 (25SEP2017)	8.1.5	Updated categories for microbial infection and added rules for handling microbial infection data.
3.0 (25SEP2017)	8.1.5 8.2.2.3	GST-alpha measured using two separate kits. Quartiles will be calculated separately for the different kits
3.0 (25SEP2017)	8.1.5	Added clarification that subgroup summary tables will also be presented for ITT Part 1 Interim Set and ITT Part 2 Set
3.0 (25SEP2017)	8.2.1	For model convergence issues, site will be removed from the model and documented.

Version (date)	Section	Summary of change

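### SAP 8.1.1 sets a 5% rejection level beside one-sided p-values without saying the 5% is two-sided; read literally, this contradicts the design's one-sided 2.5%

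*SAP*

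**What the plan says.** SAP 8.1.1 uses a closed test. The single hypothesis is "rejected at the 5% significant level if it and all intersection hypotheses involving it are all rejected at the 5% significance level". The two p-values in the inverse normal statistic "are the one-sided p-values from interim analysis at Part 1 and from Part 2, respectively", and the Dunnett-adjusted Part 1 p-value for the intersections is also one-sided. On reporting, the section says: "The one-sided p-value for the combined analysis will be presented". It does not say whether the 5% is one-sided or two-sided.

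The level is set elsewhere in two forms:

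- SAP 4.1, and protocol 7.4 in the same terms, say of the simulations that "the 1-sided type I error rate is 2.4% (and hence is well controlled at the 1-sided 2.5% significance level").
- SAP Section 4, under Statistical Analysis, says: "All statistical tests will be two-sided and performed using a 5% significance level". It allows exceptions where the plan specifically states one. The next sentence introduces the combination test and points to 8.1.1. Protocol 7.7 has the same default without the exception: "All statistical tests will be 2-sided and performed using a 5% significance level".

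Protocol 7.7.1 describes the closed test at a level alpha and gives no number. The SAP change history for version 3.0 records: "Clarification added that the p-values used in the equation for the combination test are 1-sided p-values". SAP Section 12, which lists changes from the planned analysis, records no change of alpha.

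SAP 8.2.1 makes the comparison of RRT incidence formal "if a statistically significant result is obtained from the combination test analysis of the primary endpoint".

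**The concern.** The only p-value that 8.1.1 defines for the combined test is one-sided, and the only level it states is 5%. Comparing one with the other means rejecting when the statistic exceeds 1.645. The design was justified at one-sided 2.5%, which means exceeding 1.960. A combined one-sided p between 0.025 and 0.05 is therefore a positive primary result under 8.1.1 read literally, and not significant at the level on which the design rests.

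Two things depend on the threshold: the conclusion on the primary endpoint, and whether RRT incidence is tested formally. The stated 2.4% type I error and the stated power are also at stake, because they apply at only one of the two thresholds. By the current SAP version the interim analysis had been run (8.1.4), so the success threshold should need no interpretation.

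**Working it through.** **Inputs (SAP 4.1 and 8.1.1, protocol 7.4).** Part 1 has 4 groups of n1 = 30 and Part 2 has 2 groups of n2 = 85. The SD is 49 mL/min, the placebo mean 60, and the recAP means lie between 60 and 79. An effective dose is one with a mean of 69.5. SAP 11 stops the study if all three one-sided Part 1 p-values exceed 0.8.

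**Statistic.** Z = √(30/115)·Φ⁻¹(1 − p1) + √(85/115)·Φ⁻¹(1 − p2), with weights 0.511 and 0.860. p2 is the same for every hypothesis. The Dunnett-adjusted p1 over three doses is the largest of the Part 1 p-values, so the three-dose intersection decides the closed test.

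**Thresholds.** One-sided 2.5%, equivalent to two-sided 5% in the direction of benefit, gives 1.960. One-sided 5% gives 1.645.

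**Simulation.** The best observed dose goes forward. Part 1 uses a pooled-variance t statistic on 4 × 29 = 116 df with the one-sided Dunnett adjustment; Part 2 uses a t test on 2 × 84 = 168 df. The futility rule is applied, and there is no site effect and no missing data. There were 1,000,000 runs under the null and 200,000 per alternative. The documents mention seven scenarios without listing them, so the six alternatives below are assumed.

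| Means: placebo/low/mid/high | Stated in SAP 4.1 | Reject at 1.960 | Reject at 1.645 | Difference (points) |
|---|---|---|---|---|
| 60/60/60/60 | 2.4% | 2.49% | 4.98% | 2.5 |
| 60/60/79/79 | 79–86% | 81.5% | 88.3% | 6.8 |
| 60/69.5/79/79 | 79–86% | 79.2% | 86.5% | 7.3 |
| 60/79/79/79 | 79–86% | 85.6% | 91.7% | 6.1 |
| 60/60/60/79 | 66–67% | 69.5% | 77.1% | 7.6 |
| 60/60/69.5/79 | 66–67% | 67.1% | 75.7% | 8.5 |
| 60/69.5/69.5/79 | 66–67% | 65.6% | 74.7% | 9.1 |

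Differences were taken before rounding. Every rejection at 1.960 is also a rejection at 1.645, so the last column is the share of trials in which the two readings give different primary results.

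**Reproducing the plan's figures.** The stated 2.4% comes from 50,000 runs, with a Monte Carlo standard error of √(0.024 × 0.976/50,000), about 0.07 points. The gap to 2.49% is compatible with simulation error and rounding; 4.98% is not. At 1.960, five of the six alternatives match the stated power within 1 point. The exception is 60/60/60/79, at 69.5%, or 68.9% if only rejections with a truly effective selected dose count. At 1.645 only 60/69.5/79/79 comes near its stated range, and only near the top of it. A second simulation with 400,000 runs per scenario agreed within 0.2 points throughout.

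**Fixed-design cross-check.** With 115 per arm and a difference of 19, power = Φ(19/(49·√(2/115)) − z) = Φ(2.940 − z). This gives 83.7% at z = 1.960 and 90.2% at z = 1.645.

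**The case against.** The strongest reply is that the documents, read together, give one rule. SAP Section 4 sets two-sided 5% and sends the reader to 8.1.1 in the next sentence, so the 5% there takes its sidedness from the default. Protocol 7.7 sets the same default with no exception clause. The inverse normal formula takes directional p-values whatever the overall level, so one-sided inputs do not by themselves imply a one-sided 5% test. No passage compares the combined p-value with 0.05 or mentions 1.645. The stated error rate and power are reproduced at 1.960 and not at 1.645. If the gate fails, RRT incidence is still analysed and only its label changes to exploratory.

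Most of this stands, and it is why one-sided 2.5% is the probable intent. The disagreement rates in the table apply only if someone follows the literal reading; they do not measure how likely that is.

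It does not remove the gap. The SAP default gives way where the plan states otherwise, and 8.1.1 does state one-sided. The reader must then infer that the switch to one-sided also halves the 5%, and no sentence says so. Anyone applying 8.1.1 to the only combined p-value it defines would double the type I error. The same SAP does put sidedness beside a threshold elsewhere: the futility rule in Section 11 says its 0.8 is one-sided.

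**Conclusion.** The concern holds. The decision rule for the primary endpoint does not state its level unambiguously where it is applied and, read literally, it conflicts with the one-sided 2.5% in SAP 4.1 and protocol 7.4. The probable intent can be recovered from the rest of the documents, so nothing here shows that alpha was changed. The likeliest explanation is that version 3.0 clarified the p-values as one-sided and left the 5% unqualified.

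Under the literal reading, type I error is 5.0% in place of 2.5%. The primary conclusion would differ in 2.5% of null trials, in about 6 to 7% of trials when the mid and high doses are both strong, and in about 8 to 9% when only the high dose is. The doubling under the null follows directly from the two critical values. The other rates rest on the six assumed scenarios, exact group sizes of 30 and 85, selection of the best observed dose, no site effect and complete data. This should be corrected because it concerns the primary threshold and the gate to formal RRT testing.

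**What to change.** In SAP 8.1.1, replace the 5% level with: *the single hypothesis and every intersection hypothesis involving it are each tested at one-sided 2.5%, with rejection if the combined one-sided p-value is at most 0.025 (statistic at least 1.960)*.

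In SAP 8.2.1, add a cross-reference saying that this threshold opens formal testing of RRT incidence. This is a convenience, since 8.2.1 already ties the gate to the combination test.

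The cost is one sentence and one cross-reference. The design, data and sample size do not change, and the rule then matches the level at which the error rate and power were simulated.
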